3.1.4.1. Local Reactions

The local reactions assessed and reported in the e-diary are pain at the injection site, redness, and swelling, from Day 1 through Day 7 after each dose, where Day 1 is the day of each dose. This section describes derivations with details for the assessment of local reactions: presence, severity level, duration, and onset day.

Presence or Absence

For each local reaction and any local reaction on any day, Table 3 defines the algorithm to derive the presence of a reaction (yes or no) during the interval from Day 1 through Day 7, where Day 1 is the day of each dose.

Table 3. Derived Variables for Presence of Each and Any Local Reaction Within 7 Days for Each Dose

Variable	Yes (1)	No (0)
Presence of each local reaction on any day	Participant reports the reaction as “yes” on any day (Day 1 through Day 7).	Participant reports the reaction as “no” on all 7 days (Day 1 through Day 7) or as a combination of “no” and missing on all 7 days (Day 1 through Day 7).
Presence of any local reaction on any day	Participant reports any local reaction as “yes” on any day (Day 1 through Day 7).	For all 3 local reactions, participant reports “no” on all 7 days (Day 1 through Day 7) or a combination of “no” and missing on all 7 days (Day 1 through Day 7).

Note: Missing e-diary data will not be imputed. Participants with no e-diary data reported will not be included in the e-diary summaries.

Severity and Maximum Severity

Redness and swelling will be measured and recorded in measuring device units (range: 1 to 21) and then categorized during analysis as absent, mild, moderate, or severe based on the grading scale in [Table 4](#). Measuring device units can be converted to centimeters according to the following scale: 1 measuring device unit = 0.5 cm. Pain at the injection site will be assessed by the participant as mild, moderate, or severe according to the grading scale in [Table 4](#).

If a Grade 3 local reaction is reported in the reactogenicity e-diary, a telephone contact should occur to ascertain further details and determine whether a site visit is clinically indicated. Only an investigator or medically qualified person is able to classify a participant's local reaction as Grade 4. If a participant experiences a confirmed Grade 4 local reaction, the investigator must immediately notify Pfizer and, if it is determined to be related to the administration of the study intervention, further vaccinations will be discontinued in that participant.

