
Table 4. Grading Scales for Local Reactions

Local Reaction	Mild (Grade 1)	Moderate (Grade 2)	Severe (Grade 3)	Potentially Life Threatening (Grade 4 ^a)
Pain at the injection site	Does not interfere with activity	Interferes with activity	Prevents daily activity	Emergency room visit or hospitalization for severe pain
Redness	>2.0 cm to 5.0 cm (5 to 10 measuring device units)	>5.0 cm to 10.0 cm (11 to 20 measuring device units)	>10 cm (≥ 21 measuring device units)	Necrosis or exfoliative dermatitis
Swelling	>2.0 cm to 5.0 cm (5 to 10 measuring device units)	>5.0 cm to 10.0 cm (11 to 20 measuring device units)	>10 cm (≥ 21 measuring device units)	Necrosis

- a. Only an investigator or medically qualified person is able to classify a reaction as Grade 4; therefore, a confirmed Grade 4 should be reported as an AE in the case report form.

For each local reaction after each dose, the maximum severity grade will be derived for the e-diary collection period (Day 1 through Day 7, where Day 1 is the day of each dose) as follows:

maximum severity grade = highest grade (maximum severity) within 7 days after vaccination (Day 1 through Day 7) among the severity grades reported for that local reaction in the e-diary.

Duration (First to Last Day Reported)

The duration (days) of each local reaction will be calculated as the number of days from the start of the first reported reaction to the resolution of the last reported reaction, inclusive. Resolution is defined as the last day on which the reaction is recorded in the e-diary if the reaction lasted 7 days or less, or the day the reaction ended if it continued beyond Day 7 (the latter will be collected on the CRF). If there is no known date when the reaction ended, then duration will be missing (unknown). However, if a reaction is ongoing at the time of a subsequent dose, the end date/day for the ongoing event would be the date/day that the next dose is administered, which will be used for the duration computation. Participants with no reported reaction have no duration.

Onset Day

The onset day of each local reaction will be derived. Onset day is defined as the first day of reporting the reaction with any severity after vaccination.

For the onset day of each local reaction, if participants report a change in severity of the local reaction, only the first day of reporting that specific local reaction will be counted.

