3.1.4.2. Systemic Events (Systemic Event Symptoms and Fever)

The systemic events assessed and recorded in the e-diary are fever, fatigue, headache, chills, vomiting, diarrhea, new or worsened muscle pain, and new or worsened joint pain from Day 1 through Day 7, where Day 1 is the day of each dose. The derivations for systemic events will be handled similarly to the way local reactions are handled for presence of event, severity level, duration, and onset day (see [Section 3.1.4.1](#)). Maximum temperature range over the period from Day 1 through Day 7 will be mapped into the ranges described in [Table 6](#) for summary of maximum temperature.

The systemic events will be assessed by the participant as mild, moderate, or severe according to the grading scale in Table 5.

If a Grade 3 systemic event is reported in the reactogenicity e-diary, a telephone contact should occur to ascertain further details and determine whether a site visit is clinically indicated. Only an investigator or medically qualified person is able to classify a participant's systemic event as Grade 4. If a participant experiences a confirmed Grade 4 systemic event, the investigator must immediately notify Pfizer and, if it is determined to be related to the administration of the study intervention, further vaccinations will be discontinued in that participant.

Table 5. Grading Scales for Systemic Events

Systemic Event	Mild (Grade 1)	Moderate (Grade 2)	Severe (Grade 3)	Potentially Life Threatening (Grade 4)
Fatigue	Does not interfere with activity	Some interference with activity	Prevents daily routine activity	Emergency room visit or hospitalization for severe fatigue
Headache	Does not interfere with activity	Some interference with activity	Prevents daily routine activity	Emergency room visit or hospitalization for severe headache
Chills	Does not interfere with activity	Some interference with activity	Prevents daily routine activity	Emergency room visit or hospitalization for severe chills
Vomiting	1-2 times in 24 hours	>2 times in 24 hours	Requires IV hydration	Emergency room visit or hospitalization for hypotensive shock
Diarrhea	2 to 3 loose stools in 24 hours	4 to 5 loose stools in 24 hours	6 or more loose stools in 24 hours	Emergency room visit or hospitalization for severe diarrhea

Table 5. Grading Scales for Systemic Events

Systemic Event	Mild (Grade 1)	Moderate (Grade 2)	Severe (Grade 3)	Potentially Life Threatening (Grade 4)

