New or worsened muscle pain	Does not interfere with activity	Some interference with activity	Prevents daily routine activity	Emergency room visit or hospitalization for severe new or worsened muscle pain
New or worsened joint pain	Does not interfere with activity	Some interference with activity	Prevents daily routine activity	Emergency room visit or hospitalization for severe new or worsened joint pain

Abbreviation: IV = intravenous.

Oral temperature will be collected in the evening, daily, for 7 days following each dose (Days 1 through 7, where Day 1 is the day of each dose) and at any time during the 7 days that fever is suspected. Fever is defined as an oral temperature of $\geq 38.0^{\circ}\text{C}$ (100.4°F). The highest temperature for each day will be recorded in the e-diary.

Temperatures will be measured and recorded to 1 decimal place. Temperatures recorded in degrees Fahrenheit will be programmatically converted to degrees Celsius first for reporting. Temperatures $< 35.0^{\circ}\text{C}$ and $> 42.0^{\circ}\text{C}$ will be excluded from the analysis. Fever will be grouped into ranges for the analysis according to Table 6.

If a fever of $\geq 39.0^{\circ}\text{C}$ (102.1°F) is reported in the reactogenicity e-diary, a telephone contact should occur to ascertain further details and determine whether a site visit is clinically indicated. Only an investigator or medically qualified person is able to confirm a participant's fever as $> 40.0^{\circ}\text{C}$ ($> 104.0^{\circ}\text{F}$). If a participant experiences a confirmed fever $> 40.0^{\circ}\text{C}$ ($> 104.0^{\circ}\text{F}$), the investigator must immediately notify Pfizer and, if it is determined to be related to the administration of the study intervention, further vaccinations will be discontinued in that participant.

Table 6. Ranges for Fever

≥ 38.0 - 38.4°C (100.4 to 101.1°F)
> 38.4 - 38.9°C (101.2 to 102.0°F)
> 38.9 - 40.0°C (102.1 to 104.0°F)
$> 40.0^{\circ}\text{C}$ ($> 104.0^{\circ}\text{F}$)

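### As written, maximum severity of local reactions and non-fever systemic events comes from e-diary grades only, so an investigator-confirmed Grade 4 would normally be displayed as Grade 3 or lower

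*SAP*

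**What the plan says.** SAP 3.1.4.1 defines the maximum severity grade for a local reaction as the highest grade within Day 1 to Day 7 "among the severity grades reported for that local reaction in the e-diary". SAP 3.1.4.2 says systemic events are derived in a similar way, severity level included.

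The grades available from the participant are these:

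- Redness and swelling are measured in device units from 1 to 21 and "then categorized during analysis as absent, mild, moderate, or severe".
- "Pain at the injection site will be assessed by the participant as mild, moderate, or severe".
- "The systemic events will be assessed by the participant as mild, moderate, or severe".

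SAP Tables 4 and 5 nevertheless carry a Grade 4 column, and the text with each table says that only an investigator or medically qualified person may assign that grade. For local reactions, Table 4 footnote a adds the recording route: "therefore, a confirmed Grade 4 should be reported as an AE in the case report form". Table 5 has no such footnote.

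The derived grade feeds the tables by maximum severity (SAP 6.1.2.1.1 and 6.1.2.2.1) and the bar charts split by maximum severity (SAP 6.1.2.1.2 and 6.1.2.2.2). Fever is outside this point, because e-diary temperature is mapped to ranges and the top range in Table 6 lies above 40.0 °C.

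**The concern.** The grading scale has four levels, but the stated derivation draws on a source that normally supplies three. A reader of the primary reactogenicity displays who sees no Grade 4 events could take this as a finding about the vaccine, when it would follow from the algorithm.

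Site input also works in one direction only. SAP 6.1.2.1.1 and 6.1.2.2.1 remove confirmed e-diary errors, so follow-up by the site can take a diary grade away. Nothing in the available text lets it raise one. Yet the SAP already goes outside the e-diary for another attribute of the same reactions: duration runs to the last e-diary day "or the day the reaction ended if it continued beyond Day 7 (the latter will be collected on the CRF").

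At stake is the accuracy of the severity split in a primary safety display. The inferential part of the trial is not involved.

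**Working it through.** The plan states no figure for this point, so there is none to reproduce. The check applies the rule to every admissible e-diary value and then sizes one misgraded case.

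**1. Top of the e-diary scale.** For redness and swelling, the maximum of 21 units × 0.5 cm per unit = 10.5 cm. This exceeds 10 cm and is severe (Grade 3) in Table 4. Grade 4 in Table 4 is necrosis, or for redness necrosis or exfoliative dermatitis, which a length cannot express. For pain and the seven non-fever systemic events the top participant category is severe, again Grade 3.

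**2. The rule applied to a participant with a confirmed Grade 4.**

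| E-diary, Day 1–7 | Maximum under the SAP rule | Maximum if the confirmed grade counts |
|---|---|---|
| Severe on 3 days, absent on 4 | 3 | 4 |
| Moderate on 2 days, absent on 5 | 2 | 4 |
| Absent on 1 day, missing on 6 | No reaction | 4 |

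With no e-diary data at all the participant drops out, since "Participants with no e-diary data reported will not be included in the e-diary summaries".

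**3. Size per case.** The numbers are planned randomized (Protocol 4.1), with pooled US lots = 3 × 340 = 1020. The proportion is 1/N. The 95% upper limit is Clopper-Pearson, the method the SAP uses. With no case it is 1 − 0.025^(1/N); for N = 340 this gives 1 − 0.025^(1/340) = 1.08%. With one case it is the 0.975 quantile of Beta(2, N − 1).

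| Group | N | 1/N | Upper limit, 0 cases | Upper limit, 1 case |
|---|---|---|---|---|
| One US lot, or 20 µg | 340 | 0.29% | 1.08% | 1.63% |
| EU lot | 170 | 0.59% | 2.15% | 3.23% |
| Pooled US lots | 1020 | 0.10% | 0.361% | 0.545% |
| One booster arm | 30 | 3.3% | 11.6% | 17.2% |

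The single case is an assumption made for illustration. Denominators limited to participants with e-diary data will be somewhat smaller.

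**4. What the AE route shows.** SAP 6.1.2.3.1 tabulates AEs by system organ class and preferred term. SAP 6.1.2.3.2 adds related AEs and severe AEs. AE intensity is a different scale: in Protocol 10.3.3, Grade 4 means life-threatening consequences, whereas Tables 4 and 5 reach Grade 4 for an emergency room visit or hospitalization for, say, severe pain or fatigue. These summaries therefore keep the event but do not display its grade on the solicited scale. A case that meets the hospitalization criterion in Protocol 10.3.2 also enters the SAE tables.

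**The case against.** The best defence is that the split is deliberate. Protocol 8.2 and 8.2.2 describe reactogenicity as self-collected e-diary reports that are transferred for analysis. Footnote a then sends what the participant cannot grade to the AE page. Keeping participant-reported grades apart from investigator-assessed events is coherent, and much of this stands. It means that Protocol 9.4.2, which promises presentation by severity, does not contradict the SAP. It also makes a listing an acceptable remedy. It does not explain a scale with a Grade 4 column beside displays that are not said to stop at Grade 3, nor the lack of a recording footnote for systemic events.

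Three stronger readings are tempting, and the documents do not support them:

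- A reader might infer that Grade 4 can never appear in these displays. Protocol 8.12 covers a suspected Grade 4 reported in the e-diary and then confirmed by telephone or visit. The maximum-severity rule sets no explicit cap. The limit follows from the participant scale, which sits awkwardly with 8.12.
- A reader might infer that no planned summary shows the grade. The SAP contents list sections 3.1.4.4 and 3.1.4.5 on AEs and SAEs, but their text was not in the copy available for this review. The statement can cover only the sections that could be read.
- A reader might take the 0.0% to 4.6% of severe reactions in the earlier study (Protocol 2.3) as a guide to Grade 4 frequency. It is a rate of severe reactions and gives no Grade 4 rate.

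**Conclusion.** The point holds as a minor one. On the rule as stated, investigator confirmation does not enter maximum severity, so a confirmed Grade 4 local reaction or non-fever systemic event would be shown at its e-diary grade, normally 3 or lower. The event is not lost, because it remains available through AE and SAE recording. No hypothesis test, power statement or immunogenicity result changes.

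The effect is one participant per case: at most 0.59% of a primary-study arm and 3.3% of a booster arm at planned numbers. Cases may be few or none.

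The conclusion assumes that the e-diary offers only the participant grades named in SAP 3.1.4.1 and 3.1.4.2, and that neither the table shells nor SAP 3.1.4.4 and 3.1.4.5, which could not be consulted, bring the confirmed grade back.

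**What to change.** For local reactions and non-fever systemic events, in participants with e-diary data for that dose, define maximum severity as the higher of the e-diary grade and any investigator-confirmed Grade 4 on the Table 4 or 5 scale reached on Day 1 to Day 7. Take the confirmed grade from the AE page or from the unscheduled visit assessment page of the CRF (Protocol 8.12), link it to reaction and dose at blinded data review, and give the displays a Grade 4 category.

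Keep the e-diary denominator as the SAP has it. Adding participants without e-diary data only when they had a Grade 4 would make the denominator depend on the outcome. Footnote or list such cases by reaction, dose and arm.

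At minimum, state that the displays stop at Grade 3 and list all confirmed Grade 4 cases by reaction, dose and arm.

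In either case, apply the footnote a recording route to Table 5, and reconcile Protocol 8.12 with SAP 3.1.4.1 and 3.1.4.2 on whether the e-diary can hold a suspected Grade 4.

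The cost is SAP wording and a small linking step, since the documents do not show whether the CRF pages identify the solicited-scale grade by reaction and dose. The full version also mixes participant-reported and investigator-assessed grades in one display, which needs a footnote.

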3.1.4.2. Systemic Events (Systemic Event Symptoms and Fever)

The systemic events assessed and recorded in the e-diary are fever, fatigue, headache, chills, vomiting, diarrhea, new or worsened muscle pain, and new or worsened joint pain from Day 1 through Day 7, where Day 1 is the day of each dose. The derivations for systemic events will be handled similarly to the way local reactions are handled for presence of event, severity level, duration, and onset day (see [Section 3.1.4.1](#)). Maximum temperature range over the period from Day 1 through Day 7 will be mapped into the ranges described in [Table 6](#) for summary of maximum temperature.

The systemic events will be assessed by the participant as mild, moderate, or severe according to the grading scale in Table 5.

If a Grade 3 systemic event is reported in the reactogenicity e-diary, a telephone contact should occur to ascertain further details and determine whether a site visit is clinically indicated. Only an investigator or medically qualified person is able to classify a participant's systemic event as Grade 4. If a participant experiences a confirmed Grade 4 systemic event, the investigator must immediately notify Pfizer and, if it is determined to be related to the administration of the study intervention, further vaccinations will be discontinued in that participant.

Table 5. Grading Scales for Systemic Events

Systemic Event	Mild (Grade 1)	Moderate (Grade 2)	Severe (Grade 3)	Potentially Life Threatening (Grade 4)
Fatigue	Does not interfere with activity	Some interference with activity	Prevents daily routine activity	Emergency room visit or hospitalization for severe fatigue
Headache	Does not interfere with activity	Some interference with activity	Prevents daily routine activity	Emergency room visit or hospitalization for severe headache
Chills	Does not interfere with activity	Some interference with activity	Prevents daily routine activity	Emergency room visit or hospitalization for severe chills
Vomiting	1-2 times in 24 hours	>2 times in 24 hours	Requires IV hydration	Emergency room visit or hospitalization for hypotensive shock
Diarrhea	2 to 3 loose stools in 24 hours	4 to 5 loose stools in 24 hours	6 or more loose stools in 24 hours	Emergency room visit or hospitalization for severe diarrhea

Table 5. Grading Scales for Systemic Events

Systemic Event	Mild (Grade 1)	Moderate (Grade 2)	Severe (Grade 3)	Potentially Life Threatening (Grade 4)
New or worsened muscle pain	Does not interfere with activity	Some interference with activity	Prevents daily routine activity	Emergency room visit or hospitalization for severe new or worsened muscle pain
New or worsened joint pain	Does not interfere with activity	Some interference with activity	Prevents daily routine activity	Emergency room visit or hospitalization for severe new or worsened joint pain

Abbreviation: IV = intravenous.

Oral temperature will be collected in the evening, daily, for 7 days following each dose (Days 1 through 7, where Day 1 is the day of each dose) and at any time during the 7 days that fever is suspected. Fever is defined as an oral temperature of $\geq 38.0^{\circ}\text{C}$ (100.4°F). The highest temperature for each day will be recorded in the e-diary.

Temperatures will be measured and recorded to 1 decimal place. Temperatures recorded in degrees Fahrenheit will be programmatically converted to degrees Celsius first for reporting. Temperatures $< 35.0^{\circ}\text{C}$ and $> 42.0^{\circ}\text{C}$ will be excluded from the analysis. Fever will be grouped into ranges for the analysis according to Table 6.

If a fever of $\geq 39.0^{\circ}\text{C}$ (102.1°F) is reported in the reactogenicity e-diary, a telephone contact should occur to ascertain further details and determine whether a site visit is clinically indicated. Only an investigator or medically qualified person is able to confirm a participant's fever as $> 40.0^{\circ}\text{C}$ ($> 104.0^{\circ}\text{F}$). If a participant experiences a confirmed fever $> 40.0^{\circ}\text{C}$ ($> 104.0^{\circ}\text{F}$), the investigator must immediately notify Pfizer and, if it is determined to be related to the administration of the study intervention, further vaccinations will be discontinued in that participant.

Table 6. Ranges for Fever

≥ 38.0 - 38.4°C (100.4 to 101.1°F)
> 38.4 - 38.9°C (101.2 to 102.0°F)
> 38.9 - 40.0°C (102.1 to 104.0°F)
$> 40.0^{\circ}\text{C}$ ($> 104.0^{\circ}\text{F}$)

3.1.4.3. Use of Antipyretic/Analgesic Medication

The use of antipyretic/analgesic medication is also recorded in the e-diary from Day 1 through Day 7, where Day 1 is the day of each dose. For the use of antipyretic/analgesic medication from Day 1 through Day 7 after each dose, the following endpoints and variables will be derived for analysis following the same rules as for local reactions (see [Section 3.1.4.1](#)), where applicable.

3.2. Secondary Endpoints

3.2.1. Secondary Immunogenicity Endpoints

- Full-length S-binding IgG levels at baseline (before Dose 1) and 1 month after Dose 2 for participants receiving a 30- μ g dose from different manufacturing lots (US and EU)
- Fold rises in full-length S-binding IgG levels from baseline (before Dose 1) to 1 month after Dose 2 for participants receiving a 30- μ g dose from different manufacturing lots (US and EU)
- SARS-CoV-2 neutralizing titers at baseline (before Dose 1) and 1 month after Dose 2 for participants receiving 30- μ g or 20- μ g doses (prepared from the same manufacturing lot)
- Fold rises in SARS-CoV-2 neutralizing titers from baseline (before Dose 1) to 1 month after Dose 2 for participants receiving 30- μ g or 20- μ g doses (prepared from the same manufacturing lot)

Fold rises will be calculated for each participant by taking the ratio of titers or IgG concentrations from 1 month after Dose 2 to baseline.

3.3. Other Endpoints

Not applicable.

3.4. Baseline and Other Variables

Measurements or samples collected prior to Dose 1 are considered the baseline data for the assessments.

3.4.1. Demographics, Medical History, and Physical Examination

Primary Study

The demographic variables are age at Dose 1 (in years), sex (male or female), race (black/African American, American Indian or Alaskan native, Asian, Native Hawaiian or other Pacific Islander, white, multiracial, and not reported), and ethnicity (Hispanic/Latino, non-Hispanic/non-Latino, and not reported). In cases where more than 1 category is selected for race, the participant would be counted under the category “multiracial” for analysis.

Age at Dose 1 (in years) will be derived based on the participant’s birthday. For example, if the vaccination day is 1 day before the participant’s 19th birthday, the participant is considered to be 18 years old. For participants who were randomized but not vaccinated, the randomization date will be used in place of the date of Dose 1 for the age calculation. If the randomization date is also missing, then the informed consent date will be used for the age calculation.

Medical history will be categorized according to MedDRA.

If the clinical assessment indicates that a physical examination is necessary to comprehensively evaluate the participant at Visit 1, a physical examination will be performed and any findings recorded in the source documents and, if clinically significant, it will be recorded on the medical history CRF.

Booster Study

The demographic variables for the booster study are defined as in the primary study except for age at Dose 3 (in years), which is derived using the date of birth and the Dose 3 date.

